**Methodology (Continued):**

Starting with Amendment 6, subjects receiving upadacitinib 15 mg and 30 mg QD will receive open-label upadacitinib 15 mg QD. Subjects receiving MTX will receive open-label MTX.

The study duration will include a 35-day screening period, a 48-week randomized, double-blind, parallel-group, active-comparator controlled treatment period (Period 1); a 212-week extension period (blinded until the last subject completes the last visit of Period 1) (Period 2); and a 30-day follow-up (call or site visit).

Subjects will be randomized in a 1:1:1 ratio to treatment Groups 2, 3 and 4 below, except for subjects from Japan, who will be randomized in a 2:1:1:1 ratio to Groups 1, 2, 3 and 4:

- Group 1: Upadacitinib 7.5 mg QD monotherapy (subjects in Japan only; N = 75)
- Group 2: Upadacitinib 15 mg QD monotherapy (N = 300) (includes 37 subjects from Japan)
- Group 3: Upadacitinib 30 mg QD monotherapy (N = 300) (includes 37 subjects from Japan)
- Group 4: MTX monotherapy (N = 300) (includes 37 subjects from Japan)

Each subject will be instructed to take 2 capsules once weekly (MTX and/or matching placebo) and 1 tablet once daily (upadacitinib or matching placebo) to maintain blinding. MTX and matching placebo will be assigned via the Interactive Response Technology (IRT) system, and distributed as identical capsules in blister packs, to provide the correct total dose for each individual subject and to maintain blinding during and after MTX titration (Period 1 and Period 2). Detailed dosing instructions can be found in the Subject Dosing Diary and Instructions. Starting with Amendment 6 subjects receiving MTX will receive open-label MTX tablets in quantities sufficient to cover their respective dose.

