#### **5.5.5.2 Blinding of Data for Data Monitoring Committee**

An external Data Monitoring Committee (DMC) comprised of persons independent of AbbVie and with relevant expertise in their field will review unblinded safety data from the ongoing study. The primary responsibility of the DMC will be to protect the safety of the subjects participating in this study.

A separate DMC charter will be prepared outside of the protocol and will describe the roles and responsibilities of the DMC members, frequency of data reviews, and relevant safety data to be assessed.

Communications from the DMC to the Study Teams will not contain information that could potentially unblind the team to subject treatment assignments.

As of September 2018, with all subjects having reached the end of Period 1, and after final review of unblinded safety data, the DMC concluded its oversight of this study.

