8.0 Study Drug Exposure and Compliance

8.1 Study Drug Exposure

The duration of exposure to study drug will be summarized for the safety analysis set by the following groups.

1. MTX monotherapy

This includes MTX exposure as monotherapy from subjects starting on MTX monotherapy censored at time of rescue to upadacitinib + MTX.

2. Any Upadacitinib 15 mg QD

This includes Upadacitinib 15 mg QD exposure from subjects starting on Upadacitinib 15 mg QD and subjects rescued from MTX to Upadacitinib 15 mg QD + MTX.

3. Upadacitinib 15 mg QD mono

This includes Upadacitinib 15 mg QD monotherapy exposure from subjects starting on Upadacitinib 15 mg QD monotherapy and censored at time of rescue to upadacitinib 15 mg QD + MTX or with addition of background csDMARD.

4. Any Upadacitinib 30 mg QD

This includes Upadacitinib 30 mg QD exposure from subjects starting on Upadacitinib 30 mg QD and subjects rescued from MTX to Upadacitinib 30 mg QD + MTX. Exposure is censored at time of dose switch from Upadacitinib 30 mg QD to Upadacitinib 15 mg QD.

5. Upadacitinib 30 mg QD mono

This includes Upadacitinib 30 mg QD monotherapy exposure from subjects starting on Upadacitinib 30 mg QD monotherapy and censored at time of rescue to upadacitinib 30 mg QD + MTX or with addition of background csDMARD. In addition, exposure is censored at time of dose switch from Upadacitinib 30 mg QD to Upadacitinib 15 mg QD.

6. Any Upadacitinib 15 mg QD switched from any Upadacitinib 30mg QD

This includes Upadacitinib 15 mg QD exposure from subjects who switched dose from Upadacitinib 30 mg QD to Upadacitinib 15 mg QD.

7. Upadacitinib 15 mg QD mono switched from Upadacitinib 30mg QD mono

This includes Upadacitinib 15 mg QD monotherapy exposure from subjects who started and remained on Upadacitinib 30 mg QD monotherapy (without rescue or addition of background csDMARD) and switched dose from Upadacitinib 30 mg QD to Upadacitinib 15 mg QD. Exposure is censored at time of addition of background csDMARD.

In addition to the groups above, the Japan sub-study has the additional groups of Any Upadacitinib 7.5 mg QD and Upadacitinib 7.5 mg QD monotherapy.

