Subjects could be blindly switched from Upadacitinib monotherapy to the combination of upadacitinib + MTX at Week 26, or could have background csDMARD added/initiated after Week 26, depending upon the CDAI response and joint counts. For subjects rescued with blinded study drug MTX at Week 26, the exposure under upadacitinib monotherapy is censored prior to the day when blinded study drug MTX is initiated. For subjects not rescued with blinded study drug MTX at Week 26 but added/initiated csDMARD as a background therapy, the exposure under the monotherapy of upadacitinib is censored prior to the day when the first dose of csDMARD is initiated.

Starting with Amendment 5.01.01 (for Japan) and Amendment 6 (for global), subjects receiving upadacitinib 30 mg QD will be switched to receiving upadacitinib 15 mg QD. Exposure to upadacitinib 30 mg QD (Groups 4 and 5) will be censored prior to the day subject received the first dose of upadacitinib 15 mg QD, and subsequent exposure to upadacitinib 15 mg QD will be summarized under separate groups (Groups 6 and 7).

The duration of exposure to study drug will be summarized for each group as specified above, with the number of subjects, mean, standard deviation, median, minimum and maximum values. In addition, the number and percentage of subjects exposed to study drug will be summarized for the following cumulative duration intervals.

- ≥ 2 weeks
- ≥ 1 month
- ≥ 3 months
- ≥ 6 months
- ≥ 9 months
- ≥ 12 months
- ≥ 18 months
- ≥ 2 years
- ≥ 2.5 years
- ≥ 3 years
- ≥ 4 years

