10.2.2 Analysis of Long Term Adverse Event Rates

Long term adverse event rates will be analyzed using event rates adjusted by cumulative exposure and will be based on the actual treatment received at the time of AE occurrence. Starting with Amendment 5.01.01 (for Japan) and Amendment 6 (for global), subjects receiving upadacitinib 30 mg QD will be switched to upadacitinib 15 mg QD. For these subjects, adverse events and exposure to upadacitinib 30 mg QD will be censored at the time of dose switch; subsequent adverse events and exposure starting the day of first dose

of upadacitinib 15 mg QD will be summarized under separate groups. The detailed treatment exposure groups, including the handling of dose switch, are described in Section 8.1.

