10.2.2.1 Overview of Adverse Events Rates per 100 Patient-Years of Study Drug Exposure

An overview of AEs per 100 patient-years of study exposure will be presented by treatment group and overall for the following AE categories.

- All TEAEs
- Treatment-emergent serious adverse events (SAEs)
- Treatment-emergent severe adverse events
- TEAEs reasonably possibly related to study drug
- TEAEs of special interest
- TEAEs leading to discontinuation of study drug
- TEAE leading to death

For this calculation, one year will be considered to be 365.25 days. For each treatment group, the numerator of the overall rate will be the total number of TEAEs reported for the event; that is, a subject can contribute more than one event to the numerator. For each treatment group, the denominator of the rates will be the total number of days exposed to study drug summed across all treated subjects divided by 365.25. The TEAE rate per 100 patient-years of exposure will be calculated as $(\text{[numerator/denominator]}) * 100$. The number of TEAEs reported (numerator), the total number of years of study drug exposure (denominator), and the TEAE rate per 100 patient-years will be presented for each treatment group and overall.

In the AE overview summary, any event with an unknown severity will be considered as severe and any AE with an unknown relationship will be considered as having "reasonable possibility" of being related to study drug. Additional TEAEs may be

considered for tabulation/summary based on recommendations from Clinical and Safety as deemed appropriate.

For TEAEs of special interest, the point estimate and 95% CI (using normal approximation) will be provided for the treatment difference in the TEAE rate per 100 patient years between each Upadacitinib dose group and the MTX group.

As a sensitivity analysis, the AE overview summary per 100 patient-years of study exposure will be repeated by exposure groups. In this summary, all AEs with an onset date after the first dose of study drug will be included, regardless of whether the AE occurred more than 30 days after the last dose of study drug. This sensitivity analysis will only be performed in final CSR.

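### The long-term AESI rate difference for 30 mg versus MTX ends 30 mg follow-up at the dose switch but not MTX follow-up, so it can differ from zero without a drug effect if event rates change over time

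*SAP*

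**What the plan says.** SAP 10.2.2.1 defines the long-term rate as number of events over pooled exposure: "the denominator of the rates will be the total number of days exposed to study drug summed across all treated subjects divided by 365.25". For AESI it then adds a point estimate and 95% CI, by normal approximation, for "the treatment difference in the TEAE rate per 100 patient years between each Upadacitinib dose group and the MTX group".

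The follow-up that counts for each group is set elsewhere:

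- **30 mg.** SAP 10.2.2: "adverse events and exposure to upadacitinib 30 mg QD will be censored at the time of dose switch". SAP 8.1 says the same of the Any 30 mg group: "Exposure is censored at time of dose switch from Upadacitinib 30 mg QD to Upadacitinib 15 mg QD". Time after the switch goes to Groups 6 and 7.
- **MTX.** SAP 8.1, Group 1: "This includes MTX exposure as monotherapy from subjects starting on MTX monotherapy censored at time of rescue to upadacitinib + MTX". No other cut is given. Under Amendment 6 MTX carries on (Protocol synopsis): "Subjects receiving MTX will receive open-label MTX".
- **Maximum duration.** The protocol synopsis gives 260 weeks.

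The only sensitivity analysis for these rates (SAP 10.2.2.1 and 10.2.2.2) adds events more than 30 days after the last dose. The one AESI contrast in which the groups share a window stops at Week 26 (SAP 10.1.1 and 10.2.1.1).

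**The concern.** Dividing by patient-years makes two groups comparable when the event rate is constant over follow-up. If it is not, the part of follow-up that is observed also matters. Here the 30 mg group gives up its late study time, and the later calendar period, while MTX subjects still on drug keep theirs. The planned difference then combines any drug effect with any change in the background rate. Its interval expresses sampling error only, so a reader cannot separate the two. The SAP neither assumes a constant rate openly nor plans a check of it. By contrast, SAP 10.1.2 summarises laboratory and vital-sign means by visit and handles post-switch visits separately. Adverse event rates get no such time structure.

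**Working it through.** **1. Plan's own figure.** 48 + 212 = 260 weeks, the longest possible MTX window. The documents give no AESI rate, event count or precision for this contrast.

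**2. When the switch can occur.** Protocol 1.1 dates Amendment 5.01.01 (Japan) 15 July 2019 and Amendment 6 16 December 2019. Protocol 5.5.5.2 says: "As of September 2018, with all subjects having reached the end of Period 1".

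- Last randomisation: 30 September 2018 minus 48 weeks is 29 October 2017; adding the 7-day visit window gives 5 November 2017.
- First randomisation: assumed 1 November 2015 (the original protocol is dated 1 October 2015).
- Outside Japan, to 16 December 2019: 771 days / 7 = Week 110 for the last subject; 1506 / 7 = Week 215 for the first.
- Japan, to 15 July 2019: 617 / 7 = Week 88; 1352 / 7 = Week 193.

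These are lower limits. Local approval and 12-weekly visits push the switch later, and SAP 7.0 notes that the visit varies by subject.

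**3. Share of the 260 weeks lost to 30 mg but open to MTX (outside Japan).** Share = 1 - switch week / 260.

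- Week 110: 58%. Week 215: 17%. Mid-enrolment, (110 + 215) / 2 = about Week 163: 37%.
- At mid-enrolment, a 6-month delay gives 28%. With no delay, yearly attrition of 10-20% gives 26-32%. A 180-day delay with 20% attrition gives about 17%.

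**4. Spurious ratio with identical drugs, switch at Week 163, no attrition or rescue.** The rate patterns are assumed.

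- Constant rate: ratio 1, gap 0.
- First-48-week rate twice the later rate: [(48×2 + 115) / 163] / [(48×2 + 212) / 260] = 1.294 / 1.185 = 1.09.
- Three times: (259 / 163) / (356 / 260) = 1.589 / 1.369 = 1.16.
- Rate doubling linearly over 260 weeks: (1 + 163/520) / 1.5 = 1.313 / 1.5 = 0.88.

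**5. Set against the planned interval.** With 300 per arm, 30 mg exposure is 300 × 163 × 7 / 365.25 = 937 patient-years and MTX exposure is 300 × 260 × 7 / 365.25 = 1,495. Half-width per 100 patient-years = 1.96 × 100 × √(λ/937 + λ/1495), with λ the yearly rate per subject.

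| Assumed MTX rate per 100 PY | Spurious gap | Half-width (equal rates) | Chance that CI excludes 0* |
|---|---|---|---|
| 0.3 | -0.04 to +0.05 | 0.45 | 5.1-5.5% |
| 1 | -0.12 to +0.16 | 0.82 | 5.4-6.6% |
| 3 | -0.37 to +0.48 | 1.41 | 6.1-9.8% |

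*Over 0-10% yearly attrition.

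**6. Wider scenarios.** Assumptions: uniform enrolment 29 February 2016 to 29 October 2017; switch at Amendment 6 plus 0 or 26 weeks and up to 12 more; dropout 0 or 10% a year; 0 or 20% of MTX subjects rescued at Week 26; rates per 100 patient-years.

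- Constant 3: gap 0.00, CI excludes zero 5.0% of the time.
- 3 rising to 6 after Week 104: -0.74 to -0.36.
- 3 falling to 1.5 after Week 104: +0.18 to +0.37.
- 6 falling to 3 after Year 1: +0.12 to +0.37.
- Constant 3 plus a calendar rise from March 2020: of 1.5, -0.55 to -0.30; of 3, -1.09 to -0.60.

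The CI excluded zero 5.2-13.6% of the time under the time-on-study patterns, and up to 29.1% under the calendar rise of 3.

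**7. After aligning the windows.** With MTX ended at the matched switch date, the gap was 0.00 in every scenario without rescue. With 20% rescue, -0.12 to +0.06 remained, because rescued subjects leave MTX and half enter Any 30 mg at Week 26.

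**The case against.** The strongest reply is about size. At rates of 1 per 100 patient-years or below, the spurious gap is a fraction of the CI half-width, and the chance of a misleading interval stays near 5%. The largest gaps need a calendar rise, and the rates are assumed throughout. That stands, and it limits the weight of the point.

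It is also fair that the SAP makes part of the imbalance visible: events and patient-years accompany each rate, switches are tabulated by visit, exposure duration is shown by group, and post-switch time is kept apart. A careful reader could notice the mismatch but could not correct for it from those tables.

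Three stronger readings are tempting, and the documents do not support them:

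- *That 30 mg will look worse on early events such as infections and safer on late ones such as malignancy or MACE.* Nothing in either document gives the time course of any AESI, so no direction can be claimed.
- *That every MTX subject is followed to Week 260.* Rescue ends MTX monotherapy exposure, and Protocol 5.4.1 stops study drug for non-response from Week 48. Week 260 is a maximum.
- *That a 30 mg versus 15 mg, or post-switch versus 30 mg, estimate is biased.* SAP 10.2.2.1 specifies differences from MTX only. Groups 6 and 7 hold only late exposure, which matters for reading their rates, but no planned difference between doses is affected.

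**Conclusion.** The mismatch is real and follows from the SAP's own rules: 30 mg is cut at the switch, MTX is not, and nothing in SAP 10.2.2 to 10.2.2.3 aligns them. The 30 mg minus MTX difference can therefore be non-zero with no drug effect when an AESI rate changes with time on study or calendar time. Under constant rates it is exactly zero.

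The distortion is small relative to the CI for rare AESI, and grows with the event rate and the steepness of the change. The switch weeks rest on the amendment dates, the September 2018 statement and an assumed first enrolment; the gaps rest on assumed rates, delay, dropout and rescue. The switch-date cut does not affect Any 15 mg versus MTX or the contrast up to Week 26. This is a cheap improvement to the long-term safety report, which SAP 11.1 says is what the current version governs. It is not a flaw that invalidates the report.

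**What to change.** In SAP 10.2.2.1 and 10.2.2.3:

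1. Keep the all-follow-up difference as planned.
2. Add a common-window 30 mg versus MTX contrast, with events and exposure in both groups cut at the same calendar date: 15 July 2019 for subjects in Japan, 16 December 2019 elsewhere. No post-switch period then enters either group.
3. Show AESI rates by time-on-study interval (0-48, 48-96, 96-144, >144 weeks) for each exposure group, including Groups 6 and 7.
4. State beside the all-follow-up 30 mg minus MTX difference that its windows are unequal.

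A truncation at Week 84, before any possible switch, may be added as a further sensitivity analysis but should not replace the main contrast. It keeps 300 × 84 × 7 / 365.25 = 483 of the 937 patient-years on 30 mg, and at a rate of 1 per 100 patient-years it widens the half-width from 0.82 to 1.96 × 100 × √(2 × 0.01/483) = 1.26. The calendar cut costs far less: 1.96 × 100 × √(2 × 0.01/937) = 0.91.

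The cost is SAP wording and one extra set of tables from dates already held, with a somewhat wider interval for the common-window contrast. The change does not cure the Week 26 rescue crossover.

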## **Discontinuation of Study Drug and Continuation of Study Participation (Period 1 and Period 2)**

Subjects may discontinue study drug treatment, but may choose to continue to participate in the study (refer to Section 5.4.1 for additional details). Subjects who prematurely discontinue study drug should complete a Premature Discontinuation visit (PD visit) as soon as possible, preferably within 2 weeks, and preferably prior to initiation of another therapy. To minimize missing data for efficacy and safety assessments, subjects who prematurely discontinue study drug treatment should continue to be followed for all regularly scheduled visits as outlined in the Activity Schedule ([Appendix D](#) and [Appendix F](#)), unless subjects have decided to discontinue study participation entirely (withdrawal of informed consent). Subjects should be advised on the continued scientific importance of their data even if they discontinue treatment with study drug early. Following discontinuation of study drug, the subject should be treated in accordance with the investigator's best clinical judgment irrespective of whether the subject decides to continue participation in the study. In addition, all future rescue- and efficacy-driven discontinuation criteria no longer apply. This includes 20% TJC/SJC calculations at Weeks 12 – 24, Weeks 36 – 40 and Week 48 and thereafter, as well as CDAI calculation

at Week 26, if applicable. If at any point a subject no longer wants to provide assessments (withdrawal of informed consent) following discontinuation of study drug, a second PD visit is not required.

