#### **6.1.4 Adverse Event Collection Period**

All AEs reported from the time of study drug administration until 30 days following discontinuation of study drug administration have elapsed will be collected, whether solicited or spontaneously reported by the subject. Subjects who discontinue study drug treatment but continue to participate in the study will have SAEs and nonserious AEs collected for the remainder of study participation. In addition, SAEs and protocol-related nonserious AEs will be collected from the time the subject signed the study-specific informed consent.

Adverse event information will be collected as shown in [Figure 5](#).

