1. MTX
2. Upadacitinib 15 mg QD
3. Upadacitinib 30 mg QD
4. Upadacitinib 15 mg QD + MTX
5. Upadacitinib 30 mg QD + MTX

For Japan sub-study, there are two additional treatment regimens:

6. Upadacitinib 7.5 mg QD
7. Upadacitinib 7.5 mg QD + MTX

Among the subjects who entered Period 2 participation (regardless of whether subject prematurely discontinued study drug in Period 1), the number and percentage of subjects who completed, and who prematurely discontinued study participation in Period 2 will be summarized. Among the subjects who entered Period 2 upon completion of study drug in Period 1, the number and percentage of subjects completed, and who prematurely discontinued study drug in Period 2 will be summarized.

For subjects who prematurely discontinued study drug or study participation, the primary reasons as well as all reasons for discontinuation will be summarized by the following categories (as collected in CRF):

- Adverse event (AE)
- Withdrew consent
- Lost to follow-up
- Lack of efficacy
- Other

Summary of Dose Switch from Upadacitinib 30 mg QD to 15 mg QD

Starting with Amendment 5.01.01 (for Japan) and Amendment 6 (for global), subjects receiving upadacitinib 30 mg QD will be switched to upadacitinib 15 mg QD. The visit at which dose switch occurs could be different for each subject. For subjects on upadacitinib 30 mg QD in Period 2, the number and percentage of subjects switching to upadacitinib 15 mg QD at each visit will be summarized.

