10.2.2.2 Overview of Adverse Events Rates per 100 Patient-Years of Study Drug Exposure

For each treatment group, the TEAE rate per 100 patient-years of exposure will be calculated overall, for each SOC and each PT, for each of the following events:

- All TEAEs
- Treatment-emergent serious adverse events (SAEs)
- Treatment-emergent severe adverse events
- TEAEs reasonably possibly related to study drug
- TEAEs leading to discontinuation of study drug
- TEAE leading to death

For this calculation, one year will be considered to be 365.25 days. For each treatment group, the numerator of the overall rate, the SOC rate, or the PT rate, will be the total number of TEAEs reported overall, for the SOC, or for the PT, respectively; that is a subject can be counted more than once overall, for a SOC, and for a PT. For each treatment group, the denominator of the rates will be the total number of days exposed to study drug summed across all treated subjects divided by 365.25. The TEAE rate per 100 patient-years of exposure will be calculated as $[(\text{numerator}/\text{denominator})]*100$. The

number of TEAEs reported (numerator), the total number of years of study drug exposure (denominator), and the TEAE rate per 100 patient-years will be presented overall, for each SOC, and for each PT for each treatment group.

As a sensitivity analysis, the AE summary per 100 patient-years of study exposure by SOC and PT will be repeated by exposure groups. In this summary, all AEs with an onset date after the first dose of study drug will be included, regardless of whether the AE occurred more than 30 days after the last dose of study drug. This sensitivity analysis will only be performed in final CSR.

10.2.2.3 Adverse Events of Special Interest Rates per 100 Patient-Years of Study Drug Exposure

The Adverse Events of Special Interest (AESI) categories will be summarized and presented for each treatment group and overall using SOC and MedDRA PT (for adjudicated cardiovascular events, the CAC adjudicated categories will be used). The AESI categories will be identified per Standard MedDRA Queries (SMQs)/Company MedDRA Queries (CMQs).

For each treatment group, the treatment-emergent Adverse Events of Special Interest (AESI) rate per 100 patient-years of exposure will be calculated overall, for each SOC and each PT, for each of the AESI listed in Section [10.2.1.6](#).

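### Two final-CSR sensitivity analyses of long-term AE rates count off-drug events but divide by on-drug time only

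*SAP*

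**What the plan says.** SAP Section 10.2.2.1 opens with the main analysis: "An overview of AEs per 100 patient-years of study exposure will be presented by treatment group and overall". It then defines that rate: "the denominator of the rates will be the total number of days exposed to study drug summed across all treated subjects divided by 365.25". For each group the tables show the event count, and "the total number of years of study drug exposure (denominator), and the TEAE rate per 100 patient-years will be presented". The main rates use treatment-emergent AEs, which Section 10.2 limits to 30 days after the last dose. Section 10.2.2.2 gives the same definition by system organ class and preferred term.

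Each section ends with a sensitivity analysis for the final CSR only. In 10.2.2.1, "all AEs with an onset date after the first dose of study drug will be included, regardless of whether the AE occurred" past that 30-day limit. In 10.2.2.2, "As a sensitivity analysis, the AE summary per 100 patient-years of study exposure by SOC and PT will be repeated by exposure groups", with the same wider set of events. Neither paragraph gives a different denominator. The exposure groups in Section 8.1 are built from duration on study drug alone. Section 10.2.2 allocates events by the treatment being taken at onset.

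Off-drug follow-up is planned. Protocol Section 5.1 says that "subjects who prematurely discontinue study drug treatment should continue to be followed for all regularly scheduled visits". Protocol Section 6.1.4 says that those who stop drug but stay in the study "will have SAEs and nonserious AEs collected for the remainder of study participation". SAP Section 7.0 expects such subjects in Period 2, which it summarises "regardless of whether subject prematurely discontinued study drug in Period 1".

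**The concern.** A rate needs events and person-time from the same interval. Here the numerator runs to the end of study participation while the denominator stops at the last dose. A subject who stops at Week 60 and stays to Week 260 can add 200 weeks of events and no time.

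Three things follow. The sensitivity rate cannot be lower than the main rate, whatever the late risk. A rise does not show excess late risk, because it mixes the amount of off-drug time with how risky that time was. Groups with more off-drug time are inflated more, which distorts comparisons with MTX. Only on-drug years are printed, so a reader cannot correct the figure. A smaller gap is that the SAP does not say which exposure group an off-drug event joins.

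**Working it through.** **Which denominator applies.** One could read 'study exposure' in the sensitivity paragraphs as time in the study. That fails, because Section 10.2.2.1 uses the same phrase for the main analysis and defines it there as days on study drug.

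**Formulas.** The plan gives no figure to reproduce, so the size is illustrated.

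- T = 260 weeks = 1,820 days (protocol synopsis).
- p = share who stop drug: 10% or 15%. SAP Section 9.1.1 gives 10-15% as a general RA-trial figure, not a five-year one.
- s = share of stoppers who stay to Week 260: 25%, 50% or 100% (assumed). Stopping times are uniform over T (assumed).
- r = off-drug risk relative to on-drug risk (assumed).
- On-drug days per subject: on = T(1 - p/2).
- Off-drug days beyond day 30: off = p·s·(T - 30)²/(2T) = p·s·880.2.
- 30-day tail of those who stay: tail = p·s·(30 - 30²/(2T)) = p·s·29.75.

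Reported rate over time-matched rate = 1 + off/on, because the events cancel. Rise over the main rate = r·off/(on + r·tail).

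**Inflation over a time-matched rate.**

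| p | s | on (days) | off (days) | 1 + off/on |
|---|---|---|---|---|
| 10% | 25% | 1,729 | 22.0 | 1.013 |
| 10% | 50% | 1,729 | 44.0 | 1.025 |
| 10% | 100% | 1,729 | 88.0 | 1.051 |
| 15% | 25% | 1,683.5 | 33.0 | 1.020 |
| 15% | 50% | 1,683.5 | 66.0 | 1.039 |
| 15% | 100% | 1,683.5 | 132.0 | 1.078 |

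Per 300 subjects, the first row is 1,420 on-drug and 18 off-drug years. The last row is 1,383 and 108.

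**Rise over the main rate.**

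| Case | r = 0 | r = 0.5 | r = 1 | r = 2 |
|---|---|---|---|---|
| p = 10%, s = 25% | 0 | 0.6% | 1.3% | 2.5% |
| p = 15%, s = 100% | 0 | 3.9% | 7.8% | 15.6% |

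Both off and tail are proportional to s, so for a given p the rise depends only on the product r·s. With p = 15%, the same 3.9% rise comes from r = 2 with 25% staying, r = 1 with 50% staying, or r = 0.5 with all staying. The table cannot tell doubled risk from halved risk.

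**Group comparison with equal true rates.** Stopping of 15% v 10% gives a false rate ratio of 1.020/1.013 = 1.007 with 25% staying, 1.013 with 50% and 1.026 with all staying. With 15% stopping in both groups and 100% v 50% staying, it is 1.078/1.039 = 1.038.

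**More or earlier stopping.** If 30% stop at Week 60 and all stay, on-drug time averages 3.83 years and off-drug time 1.15 years. A true rate of 100 per 100 patient-years is then reported as 130. With 10% stopping it is 108. These shares are assumptions too.

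**Main rates.** In the high case the stoppers' 30-day tail adds 4.46/1,683.5 = 0.3%. With completers' tails it is (4.46 + 0.85 × 30)/1,683.5 = 1.8%.

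**Check.** A simulation of 400,000 subjects (p = 15%, s = 100%, 50 events per 100 on-drug years) gave rises of 0, 3.9, 7.8 and 15.7%. Its ratio to the time-matched rate was 1.081, because it counts the 30-day tail as observed time: (132.0 + 4.46)/1,683.5 = 0.081.

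**The case against.** The strongest case is that the sensitivity paragraphs are silent on the denominator rather than wrong, and that their purpose may be modest: remove the 30-day cut-off and change nothing else. Late events could then be counted by subtracting the main table, and charging them to earlier exposure is a cautious safety convention. A pooled time-matched rate can also mute a real late harm. In the high case, doubled off-drug risk moves it by only about 7%, against 15.6% as written. Finally, the size is not anchored in the documents and only two supplementary tables are involved.

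Part of this stands. The size is illustrative, the reach is narrow, and the muting is real, which is why a separate off-drug line is preferable. The rest does not rescue the plan. With one denominator defined and the summary simply repeated, on-drug time is the natural reading. Event counts without off-drug years do not give a rate. Inflation is not cautious in a comparison: if MTX subjects had more off-drug time, the MTX rate would rise more and upadacitinib would look better. The overview being repeated includes AEs of special interest, whose main version reports rate differences from MTX.

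**Conclusion.** The concern holds. Followed as written, both sensitivity analyses report rates whose events and person-time cover different intervals. The bias is upward and grows with off-drug follow-up. It is 1.3% to 7.8% if 10-15% stop uniformly and 25-100% of them stay, with false rate ratios up to 1.038 in the contrasts tried. More or earlier stopping gives larger values. None of these sizes can be fixed from the documents.

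The main rates carry only the 30-day tail. The AESI rates in 10.2.2.3 have no such sensitivity analysis, and those in 10.2.1 use percentages of subjects. Efficacy is not involved. This should be corrected before the final CSR, but it does not threaten the main conclusions.

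**What to change.** In both sensitivity analyses, divide by time under AE observation (on-drug time plus off-drug follow-up to last study contact), over the same interval as the events counted.

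Assign off-drug events and off-drug time to each Section 8.1 exposure group the subject was still in at the last dose. Apply the Section 8.1 censoring rules (rescue, dose switch, csDMARD addition) only while the subject is on study drug. Otherwise a csDMARD started after stopping would remove the off-drug time just added.

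Preferably also print off-drug events, off-drug person-years and their rate on a separate line. In the simulated high case, doubled risk then shows as 100 v 50 per 100 patient-years.

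The cost is one or two SAP sentences and minor programming for final-CSR tables, with no new data. The sensitivity rates will come out lower than under the current wording.
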